1.1.5 Clinical Studies

Inclisiran lowers LDL-C for sustained periods while only requiring twice yearly injections resulting in effective reductions in LDL-C (50% or more) in stable ASCVD patients in as soon as 3 months after the first injection. In the double-blind, placebo-controlled, multicenter Phase III ORION trials, involving 3,655 patients (about half of which received inclisiran, n=1,833), after the initial administration of inclisiran, LDL-C levels were quickly reduced with more than 65% of patients (placebo controlled) reaching an LDL-C <70 mg/dL when used on top of a maximally tolerated statin (Ray et al 2020). Adverse events in the Phase III trials were generally similar in the inclisiran and placebo groups, although injection-site adverse events were more frequent with inclisiran than with placebo; such reactions were generally mild, and none were severe or persistent. The phase III studies with inclisiran, however, were performed in stable ASCVD patients and did not include those who had a recent ACS event.

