- Responsibilities of principal investigator: Study visits will be done by the principal investigator while routine care is performed by the participant's own treating physician. As a consequence, the treating physician will not see participants more frequently due to trial participation and will not be aware of the laboratory assessments performed in the context of the study (routine or usual care laboratory tests and changes in therapy are at their discretion).
- Open label: The study will be performed as an open-label study to mimic decision making in usual care, following from the primary objective of the study. For example, if the study would have been performed as a double-blind placebo-controlled study, it would not be possible to study the effect of inclisiran treatment on statin discontinuation as participants and investigators would not be aware of treatment allocation.
- **Duration of study period:** The study is designed as a one-year trial with a total of three inclisiran doses. The Phase III trials of inclisiran had a follow-up duration of 18 months. In the Phase II trial (ORION-1), it was shown that the second dose at Day 90 lowers LDL-C to a slightly greater level then after the initial administration (Ray et al 2017). Based on these trials, the maximum reduction in LDL-C is achieved approximately 4 to 5 months after initiation of therapy. Prior studies have shown that approximately one-third of patients discontinue statin therapy in the three years following initiation of therapy (Khunti et al 2018). A follow-up duration of one year enables: 1) observation of the steady-state LDL-C lowering effect of inclisiran, 2) observation of a meaningful difference in statin discontinuations, should such a difference exist, and 3) observation of potential differences in variables that likely require longer-term treatment of inclisiran to become apparent, such as patient reported outcomes.

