4.2 Rationale for dose/regimen and duration of treatment

Previous studies have shown that a 300 mg dose of inclisiran sodium is well tolerated and provides maximum efficacy (i.e., doses higher than 300 mg did not provide additional efficacy in LDL-C lowering). The 300 mg dose of inclisiran will be administered on Day 0, Day 90 and Day 270, consistent with the dose and dosing regimen that was studied in the Phase III trials. Modelling and simulation have demonstrated that the 300 mg dose of inclisiran results in sustained reductions in LDL-C (Ray et al 2017). A treatment duration of one year will be sufficient to assess changes in LDL-C due to inclisiran and changes in concomitant lipidlowering therapy.

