Women are considered post-menopausal and not of child bearing potential if they have had 12 months of natural (spontaneous) amenorrhea with an appropriate clinical profile (e.g., age appropriate, history of vasomotor symptoms) or have had surgical bilateral oophorectomy (with or without hysterectomy), total hysterectomy or tubal ligation at least six weeks ago. In the case of oophorectomy alone, only when the reproductive status of the woman has been confirmed by follow up hormone level assessment is she considered not of child bearing potential.

- 11. Treatment with other investigational products or devices within 30 days or five half-lives of the screening visit, whichever is longer.
 - a. Approved vaccines or vaccines used under Emergency Use Authorization should not be considered part of this exclusion criteria. Patients can receive COVID vaccines during inclisiran trials.
 - b. While use of COVID anti-viral therapies approved for use under Emergency Use Authorization would need to adhere to the washout period outlined above, prior to screening, they would not be considered as criteria for trial termination/discontinuation.
- 12. History of hypersensitivity to any of the study treatments or its excipients or to drugs of similar chemical classes.
- 13. Planned use of other investigational products or devices during the course of the study.
- 14. Any condition that according to the investigator could interfere with the conduct of the study, such as but not limited to:
 - a. Participants who are unable to communicate or to cooperate with the investigator.
 - b. Unable to understand the protocol requirements, instructions and study-related restrictions, the nature, scope, and possible consequences of the study (including participants whose cooperation is doubtful due to drug abuse or alcohol dependency).
 - c. Unlikely to comply with the protocol requirements, instructions, and study-related restrictions (e.g., uncooperative attitude, inability to return for follow-up visits, and improbability of completing the study).
 - d. Have any medical or surgical condition, which in the opinion of the investigator would put the participant at increased risk from participating in the study.
 - e. Persons directly involved in the conduct of the study.
- 15. Treatment with monoclonal antibodies directed towards PCSK9 or inclisiran within 90 days of screening.

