6.2.2 Prohibited medication

The treatments displayed in the table below are not allowed to be used simultaneously with inclisiran in the treatment arm. No modifications of therapy is required or recommended in the usual care arm.

Medication	Prohibition period	Action to be taken
Alirocumab (Praluent)	Participants randomized to inclisiran: monoclonal antibodies directed against PCSK9 are prohibited for the full duration of the study	Discontinue PCSK9 inhibitor
Evolocumab (Repatha)	Participants randomized to inclisiran: monoclonal antibodies directed against PCSK9 are prohibited for the full duration of the study	Discontinue PCSK9 inhibitor

Table 6-2 Prohibited medication

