6.7.2 Instruction for prescribing and taking study treatment

Packaging and Labeling

Investigational product [Inclisiran (KJX839), 284 mg Liquid PFS, 1.5 ml] will be provided by the sponsor. Medication labels will comply with regulatory requirements. The storage conditions will be described on the medication label.

The container closure system for the prefilled syringe consists of a Type I glass syringe with a stainless steel 27G 1/2" staked needle covered by a removable rigid needle shield and Flurotech covered bromobutyl plunger.

Table 6-4 Dose and treatment schedule

Investigational / Control Drug (Name and Strength)	Dose	Frequency and/or Regimen	
Inclisiran (KJX839), 284 mg Liquid in PFS, 1.5 mL	Inclisiran sodium 300 mg/1.5 mL (equivalent to 284 mg inclisiran), s.c. use	Initially, 90 days later, 180 days after the second dose	

Participants will be administered a single SC injection of 300 mg Inclisiran sodium for injection at predefined time points as described in the Schedule of Assessments (Table 8-1). Investigational product injection will be administered by qualified clinical study site staff under the supervision of the investigator or designee. The site of injection is the abdomen, arm or thigh. Do not inject into areas of active skin disease or injury such as sunburns, skin rashes, inflammation, tattoos or skin infections.

All kits of study treatment assigned by the IRT will be recorded in the IRT system.

7 Informed consent procedures

Eligible participants may only be included in the study after providing (witnessed, where required by law or regulation), IRB/IEC-approved informed consent.

If applicable, in cases where the participant's representative(s) gives consent (if allowed according to local requirements), the participant must be informed about the study to the extent possible given his/her understanding. If the participant is capable of doing so, he/she must indicate agreement by personally signing and dating the written informed consent document.

Informed consent must be obtained before conducting any study-specific procedures (e.g., all of the procedures described in the protocol). The process of obtaining informed consent must be documented in the participant source documents.

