Participants may be seen at any time for an unscheduled visit, e.g., if they experience deterioration or AEs that in the opinion of the Investigator/qualified site staff requires closer monitoring. The assessment(s) performed at an unscheduled visit must include at a minimum: an assessment of concomitant medications, vital signs, and an AE/SAE assessment. Any additional assessments performed are at the Investigator/qualified site staff's discretion.

Table 8-1 Assessment Schedule

Period	Screening	Treatment ¹			Unplanned	
Visit Name	Visit 1	Baseline/Visit 2	Visit 3	Visit 4	EOS/Visit 5	Unscheduled Visit
Days	-30 to -1	0	90	270	330	-
Informed Consent	Х					
Inclusion / Exclusion criteria	Х	X				
Physical Examination	S		S	S	S	
Demography	Χ					
Medical History	Χ					
ACS Medical History	Χ					
Statin Intolerance Medical History	X					
Height and Weight ²	Χ	X	X	X	Χ	
Pulse Rate	X	X	X	X	Χ	X
Blood Pressure	Χ	X	Х	Х	X	X
Prior/Concomitant medications ³	Х	X	X	Х	Х	Х
Surgical / Medical procedures	Х	Х	Х	Х	Х	Х
Urinalysis		X			Χ	
Pregnancy and assessments of fertility ⁴	Х	х	х	Х	Х	
Hematology	Х	Х			Х	
Full Clinical Chemistry		Х				
Limited Chemical Chemistry	Х		X	Х	Х	
Hepatitis Markers	Х					
Lipids and lipoproteins ⁵	Х	Х	Х	Х	Х	
Coagulation	Х	Х				
Biomarker-Lipoprotein(a)		Х	Х	Х	Х	

Period	Screening	Treatment ¹			Unplanned	
Visit Name	Visit 1	Baseline/Visit 2	Visit 3	Visit 4	EOS/Visit 5	Unscheduled Visit
Days	-30 to -1	0	90	270	330	-
Electrocardiogram (ECG)	Х					
Randomization		X				
Inclisiran Dose Administration		X	Х	Х		
IRT Transaction	Х	X	Х	Х	X	
Injection Site Reaction Assessment		X	Х	Х	X	
Clinical Outcome Assessment(s)		Х	X	Х	X	
Adverse Events	X	X	X	Х	X	Х

XAssessment to be recorded in the clinical database or received electronically from a vendor

SAssessment to be recorded in the source documentation only

¹Due to a Public Health Emergency, if participant is unable to attend in-person visit, phone or virtual visit is an acceptable alternative. At home visits by site staff or a nursing service may be used to assist with blood draws and/or study medication administration if required at this visit.

²Height only to be performed at Visits 1 and 2

³ 30 days prior to randomization

⁴All female participants of childbearing potential will have a serum pregnancy test (hCG) performed at Visit 1 (central lab). A urine pregnancy test will be conducted at the local site for remaining visits.

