8.1 Screening

A participant's eligibility for the study will be assessed during the 30 day screening period (Day -30 to Day -1). Screening is flexible in duration based on the time required for participants to be evaluated for eligibility. It is permissible to re-screen a participant if s/he fails the initial screening; however, each case must be discussed and agreed with the Sponsor on a case-by-case basis.

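### Exclusion 15 counts 90 days back from screening, so a participant could be randomized with a baseline LDL-C already lowered by inclisiran or a PCSK9 antibody

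*Protocol*

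**What the plan says.** Protocol 5.2, exclusion 15, removes patients with "Treatment with monoclonal antibodies directed towards PCSK9 or inclisiran within 90 days of screening". Amendment 04 added inclisiran to a window that already applied to the antibodies.

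The two agents have different schedules. Protocol 4.1 describes the antibodies as injected every 2 to 4 weeks. Table 6-4 gives inclisiran as "Initially, 90 days later, 180 days after the second dose", and section 1.1.5 states that "Inclisiran lowers LDL-C for sustained periods while only requiring twice yearly injections".

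Screening runs from Day -30 to Day -1 (Protocol 8.1). Baseline is not the screening value: SAP 2.1.1 takes the last value before the first dose. Several other exclusions (4, 6, 7 and 9) count back from randomization; exclusion 15 counts from screening.

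On recording, footnote 3 of Table 8-1 sets the window for prior and concomitant medication at "30 days prior to randomization". Section 6.2.1 separately asks for earlier cardiovascular and lipid-lowering drugs, but only those the participant is still taking. In the SAP (2.4.2), the table of lipid-therapy changes before baseline covers statins and bempedoic acid over 30 days.

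**The concern.** Percent change from baseline in LDL-C is the first primary variable, and the primary objective (Table 2-1) is about starting inclisiran on top of usual care. A participant already under the effect of inclisiran does not fit that question.

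With a lowered baseline the treatment contrast can move either way. If the commercial product continues in usual care, the two arms look alike. If it lapses, LDL-C rises in usual care from a low starting point and the difference is inflated.

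An antibody started after screening raises a related problem. Table 6-2 has it stopped in the inclisiran arm, while for usual care the protocol says "No modifications of therapy is required or recommended in the usual care arm". The arms would then be handled differently from a baseline that the antibody had already lowered.

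**Working it through.** **The plan's own figures.** Protocol 12.8.1 uses SD 40, difference 15, two-sided alpha 0.025 and power 0.85. Per arm, n = 2 × (2.2414 + 1.0364)² × 40² / 15² = 152.8, so 153, or 306 in total. Then 153 / 0.8 = 191.25, so 192 per arm and 384 randomized. The 242 for variable 2 (0.55 versus 0.75) also reproduces. The sample size is not in question.

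**Length of the look-back.**
- Inclisiran: 90 / 90 = 1 first interval; 90 / 180 = 0.5 of the maintenance interval.
- Antibodies: 90 / 28 = 3.2 to 90 / 14 = 6.4 dosing intervals. The length is adequate here.

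**Timing for inclisiran.** The most recent dose that clears the rule is 91 days before screening.
- Screening on Day -1: 91 + 1 = 92 days before Day 0; 180 − 92 = 88 days of the interval left.
- Screening on Day -30: 91 + 30 = 121 days before Day 0; 180 − 121 = 59 days left.

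For either agent, a start after the screening visit falls 0 to 30 days before Day 0.

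**What an exposed participant contributes.** Take an off-drug LDL-C of 150 mg/dL and the 50% reduction in Protocol 1.1, so the baseline is 75 and the patient meets the lipid criterion.
- Inclisiran arm at Day 330: (75 − 75) / 75 = 0%.
- Usual care, product continued: 0%, so no contrast.
- Usual care, effect fully worn off: (150 − 75) / 75 = +100%, a contrast of 100 points.
- If baseline is lowered by only 25% and the effect then wears off in usual care: +33.3% against −33.3%, a contrast of 66.7 points.

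**Effect on the overall difference.** With exposed share f, the difference is (1 − f) × 15 + f × (contrast among the exposed). The shares are assumptions; the documents give none. Power is for variable 1 at 153 per arm and SD 40 (planned 0.850).

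| f (number of 384) | Usual care stays on inclisiran | Power in that case | Worn off, baseline −25% | Worn off, baseline −50% |
|---|---|---|---|---|
| 1% (4) | 14.85 | 0.843 | 15.5 | 15.85 |
| 2% (8) | 14.70 | 0.835 | 16.0 | 16.7 |
| 3% (12) | 14.55 | 0.826 | 16.55 | 17.55 |
| 5% (19) | 14.25 | 0.809 | 17.6 | 19.25 |
| 10% (38) | 13.50 | 0.761 | 20.2 | 23.5 |

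At 3%: 0.97 × 15 = 14.55, and 14.55 + 0.03 × 100 = 17.55. For variable 2, if exposed participants show no difference, power falls from 0.928 to 0.896 at 5% and 0.855 at 10%.

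**Do the planned analyses isolate these participants?**
- The sensitivity analysis that drops baseline LDL-C below 70 mg/dL (SAP 2.5.5) misses exposed participants at 70 or above.
- The Per-Protocol Set (SAP 2.2) removes inclisiran use in usual care. A participant who clears exclusion 15 is not a protocol deviation, so exposure before baseline is not removed as such in either arm.
- The supplementary analysis (SAP 2.5.6) acts on events after treatment starts.
- No subgroup in SAP 2.2.1 is defined by prior PCSK9-directed therapy.

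**The case against.** The best case for the plan is that few participants can be affected and several safeguards exist. Protocol 4.1.1 expects little commercial inclisiran use in the usual-care group. Exposed patients must still meet the lipid threshold at screening. Randomization balances them on average, and baseline LDL-C is in the model. Eligibility is confirmed again at Visit 2, section 4.1.1 expects no planned change in lipid therapy at screening, and the exclusion could be read as extending past the screening date. The case in which usual care continues inclisiran is a declared intercurrent event, addressed by the Per-Protocol and supplementary analyses.

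Much of this stands, and it limits the size. It does not close the gap. The Visit 2 check applies criteria that do not mention a start after screening, and the expectation of stable therapy is rationale text, not a numbered criterion. Balance between arms does not turn an on-drug baseline into an off-drug one.

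Two stronger readings should be resisted. A reader might infer that exposed participants cannot be identified. Ongoing inclisiran falls under section 6.2.1, and medical history (8.2) or health-record and claims data (section 3) may reveal others. What may go unrecorded is an injection from a course that has lapsed. A reader might also infer that 180 days is an established washout. The protocol gives two intervals, and the look-back equals the first. It says that "the maximum reduction in LDL-C is achieved approximately 4 to 5 months after initiation of therapy", but nowhere how long the effect lasts after a last dose.

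**Conclusion.** The criterion as written allows randomization part-way through an inclisiran maintenance interval. It also leaves up to 30 days between screening and randomization without a numbered rule for either agent. For antibodies only that second gap matters. This is an issue of baseline and of what the contrast means, not a sample-size error.

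The effect is probably small. At an assumed 3% exposed, the planned 15 points becomes 14.55 if usual care stays on inclisiran, a shift of −0.45. The upper figure of 17.55, a shift of +2.55, needs a baseline lowered by 50%, every exposed usual-care participant losing the effect completely, and no other therapy making up for it.

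A reader might set the exposed against the 50% drug effect seen in stable disease and infer a symmetric shift of 0.03 × 50 = 1.5 points either way. The plan's own contrast is 15, so the shift is not symmetric: dilution is slight and inflation is the larger risk. The exposed share is not in the documents, and every figure here scales with it.

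**What to change.** Reconcile the length of the inclisiran look-back in exclusion 15 with the 180-day interval in Table 6-4, or state why a shorter period is enough for this baseline. For both agents, run the exclusion up to randomization. Change footnote 3 of Table 8-1 so that PCSK9-directed therapy is recorded over the same period.

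For participants already randomized, flag any inclisiran or antibody exposure before baseline that can be found in concomitant medication, medical history and health-record or claims data. Add to SAP 2.5.5 a sensitivity analysis that repeats both primary analyses without them, and report how many there are. If recruitment has closed, this is the part that still helps.

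The cost is one criterion, one footnote, a review of existing data and one extra run of each primary model. A few patients become ineligible; on the protocol's own expectation of minimal uptake, the number is small.

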6.1 Study treatment

All eligible participants will be randomized to receive either inclisiran + usual care or usual care (standard of care per treating physician). The following study treatment will be provided: Inclisiran (KJX839), 284 mg, 1.5 ml Liquid in a single-use prefilled syringe (PFS) for s.c. administration.

6.1.1 Investigational and control drugs

Table 6-1 Investigational and control drug

Investigational/ Control Drug (Name and Strength)	Pharmaceutical Dosage Form	Route of Administration	Supply Type	Sponsor (global or local)
Inclisiran, KJX839 284 mg 1.5 ml	PFS, Liquid for injection	s.c.	Inclisiran sodium 300 mg / 1.5 ml (equivalent to 284 mg of inclisiran)	Sponsor (local)

6.1.2 Additional study treatments

No other treatment beyond investigational drug and usual care are included in this trial.

6.1.3 Treatment arms/group

Participants will be assigned at Visit 2/Baseline to one of two treatment groups (inclisiran + usual care and usual care) in a ratio of 1:1 to require approximately 384 participants (192 participants per treatment group) to be randomized.

6.1.4 Treatment duration

The planned duration of treatment is 330 days from randomization. Participants may be discontinued from treatment at any time due to adverse events, disease progression and/or at the discretion of the investigator or the participant.

